#### **19.1.4. Analysis Populations**

Approximately 350 male and female patients at least 18 years of age with moderate or severe papulopustular rosacea with 3 or 4 [moderate to severe] on the IGA scale will be enrolled and randomized in the study with a 2:1 randomization ratio, it is anticipated that:

- 234 patients will be randomized to receive S5G4T-1, Encapsulated Benzoyl Peroxide (E-BPO) Cream, 5%
- 117 patients will be randomized to receive S5G4T-2, Vehicle Cream

The ITT population will consist of all randomized patients who were dispensed study product. The safety population will be comprised of all randomized patients who are presumed to have used the study product at least once and who provide at least one post-baseline safety evaluation.

An intent-to-treat (ITT) analysis will be conducted on all study patients. A per-protocol (PP) analysis will also be conducted. Patients will be eligible for the PP analysis if they complete the 12-week evaluation without noteworthy study protocol violations (i.e., any patient or investigator activity that could have possibly interfered with the therapeutic administration of the treatment or the precise evaluation of treatment efficacy). The PP population will include patients in the ITT population who do not meet any of the following criteria:

- Failed any of the inclusion/exclusion criteria;
- Have taken any interfering concomitant medications;
- Did not attend the Week 12 Visit;
- Missed more than 1 post baseline study visit prior to Week 12
- Have not been compliant with the dosing regimen (i.e., Patients may not miss more than five consecutive days of dosing and must take 80 to 120% of expected doses. The number of expected doses will be determined for each patient based on the length of their participation in the study);
- Out of visit window ( $\pm 4$  days) at the 12-week Visit.

Patients that discontinue from the study due to an adverse event related to study treatment or documented lack of treatment effect will be included in the PP population. Data for these subjects will not be imputed by multiple imputation but rather their data will be imputed with values consistent with their status as treatment failures. Prior to breaking the blind, other additional criteria may be added to the list to accommodate for unforeseen events that occurred during the conduct of the trial that result in noteworthy study protocol violations.

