treatment-by-analysis center interaction p-value is ≤ 0.10 , the interaction will also be included in the model). The residuals from the unranked analysis will be used to calculate the skewness p-value. The skewness p-value will determine which analysis results to report:

- i. Skewness p-value > 0.01 : Report results from the parametric (unranked) ANCOVA.
 - ii. Skewness p-value ≤ 0.01 : Report results from the non-parametric (ranked) ANCOVA.
4. If there was a significant treatment by analysis center interaction (as determined in step 1 – the pooling analysis), a sensitivity analysis will be performed as described in Section 8.1.7 to find the extreme analysis center(s). Then step 3 above will be repeated the extreme analysis center(s) removed, to confirm the treatment response.

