8.7.2 Sensitivity Efficacy Analysis

8.7.2.1 Sensitivity Analyses for Absolute Change in Lesion Count

The first sensitivity analysis for absolute change in lesion count will use a repeated measures ANCOVA, with treatment, analysis center, visit (i.e., Weeks 2, 4 and 8), and treatment group by visit interaction as independent factors and a covariate of Baseline lesion count. In this analysis, data from all post-baseline visits will be included with no imputation for missing data.

The second sensitivity analysis will use the model based multiple imputation method to impute missing data for the absolute change in lesion counts at Week 12. The multiple imputation will involve 3 principal tasks:

1. Missing values will be filled in 5 times to generate 5 complete data sets. The imputation model used will be an ANCOVA with factors of treatment group and analysis center, and a covariate of Baseline lesion count (i.e., the imputation model will be the same as the analysis model).

Syntax:

```
proc mi data=datain out=dataout seed=&seed. nimpute=5 <options>;  
  class trtpn sitegr1;  
  var trtpn baseline sitegr1 week12;  
  monotone logistic (sitegr1=trtpn baseline);  
  monotone reg (week12=trtpn baseline sitegr1);  
run;
```

2. Each complete data set will be analyzed with an ANCOVA with factors of treatment group, and analysis center, and a covariate of Baseline lesion count. Appropriate modifications will be made should the analysis be based on a non-parametric method.
3. Results from these analyses will be combined into a single inference.

One random seed will be needed to impute the inflammatory lesion counts. The following random seed has been pre-specified by using a random number generator:

Inflammatory Lesion Count Seed=1543491304

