Baseline IGA	Moderate		Severe	
	E-BPO 5% Cream (N=xxx)	Vehicle Cream (N=xxx)	E-BPO 5% Cream (N=xxx)	Vehicle Cream (N=xxx)
Inflammatory Lesion Count – Absolute Change from Baseline				
n	xxx	xxx	xxx	xxx
Mean	xx.x	xx.x	xx.x	xx.x
SD	xx.xx	xx.xx	xx.xx	xx.xx
Median	xx.x	xx.x	xx.x	xx.x
Min. to Max.	xx to xx	xx to xx	xx to xx	xx to xx
Achieving Clear or Almost Clear				
Success	xx.x%	xx.x%	xx.x%	xx.x%
Failure	xx.x%	xx.x%	xx.x%	xx.x%

^a Ethnicities of Not Reported and Unknown are not included.

Note: Multiple imputation (MCMC) used to impute missing values. Summary statistics represent average values, obtained from averaging the summary statistics generated from each imputed dataset. Negative absolute change values represent decrease from Baseline.

SOURCE: USERNAME\SPONSOR\PROJECT\JOBNAME (DATE, TIME)

Table 14.2.5.1: Sensitivity Analysis of Primary Endpoints: Absolute Change from Baseline in Inflammatory Lesion Count and Dichotomized IGA Success at Week 12
(Intent-to-Treat Population)
(Page 1 of 2)

	E-BPO 5% Cream (N=xxx)	Vehicle Cream (N=xxx)	Skewness P-Value	Treatment P-Value
Inflammatory Lesion Count – Absolute Change from Baseline				
LSMean ^a	xx.x	xx.x	x.xxx ^b	x.xxx ^a
LSSD ^a	xx.xx	xx.xx		x.xxx ^c
Achieving Clear or Almost Clear				
Success	xx.x%	xx.x%	N/A	x.xxx ^d
Failure	xx.x%	xx.x%		

^a Least squares means, standard deviations and treatment p-value from a repeated measures analysis of covariance with factors of treatment group, analysis center, visit and treatment group by visit interaction, and Baseline lesion count as a covariate. Negative least squares means values represent decrease from Baseline.

^b Skewness test based on methods presented by J.H. Zar (1984).

^c P-value from a ranked repeated measures analysis of covariance with factors of treatment group, analysis center, visit and treatment group by visit interaction, and Baseline lesion count as a covariate.

^d P-value from a repeated measures logistic regression with factors of treatment group, analysis center, visit and treatment group by visit interaction.

SOURCE: USERNAME\SPONSOR\PROJECT\JOBNAME (DATE, TIME)

Table 14.2.5.1: Sensitivity Analysis of Primary Endpoints: Absolute Change from Baseline in Inflammatory Lesion Count and Dichotomized IGA Success at Week 12
(Intent-to-Treat Population)
(Page 2 of 2)

	E-BPO 5% Cream (N=xxx)	Vehicle Cream (N=xxx)	Skewness P-Value	Treatment P-Value

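### The repeated-measures lesion-count sensitivity model fits one Baseline slope for all visits, so its reported Week 12 standard error is about 3–7% larger than with visit-specific slopes; its skewness p-value also ignores within-patient correlation

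*SAP*

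**What the plan says.** SAP 8.7.2.1 gives the repeated-measures model treatment, analysis center, "visit (i.e., Weeks 2, 4 and 8), and treatment group by visit interaction as independent factors", plus the Baseline count as a covariate. It contains no Baseline-by-visit term and names no covariance structure. On the data it says that "data from all post-baseline visits will be included with no imputation for missing data". The visit list omits Week 12, which conflicts with that sentence and with the Week 12 title of Table 14.2.5.1. SAP section 10 records that treatment-by-visit was added to the protocol's model; it does not mention the Baseline slope.

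Page 1 of Table 14.2.5.1 prints three lesion-count p-values:
- the unranked treatment p-value (footnote a);
- a skewness p-value (footnote b, "Skewness test based on methods presented by" a cited textbook);
- a ranked one (footnote c: "P-value from a ranked repeated measures analysis of covariance with factors of treatment group, analysis center, visit and treatment group by visit interaction").

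SAP 8.7.1.1 says, for the primary analysis, that "The skewness p-value will determine which analysis results to report", with a cut at 0.01. SAP 8.7.3 carries that ANCOVA method to the secondary lesion endpoints. No such rule is written for the repeated-measures analysis. The one remark in 8.7.2.1 about a non-parametric method belongs to the second sensitivity analysis, the model-based imputation.

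Planned size is in Protocol 19.1.4: "234 patients will be randomized to receive S5G4T-1" and "117 patients will be randomized to receive S5G4T-2, Vehicle Cream".

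**The concern.** Change from Baseline is follow-up minus Baseline, so a patient who clears a larger share of lesions shows a change more strongly tied to the starting count. As clearance progresses, the regression of change on Baseline steepens. A model that lets treatment vary by visit but holds the Baseline slope fixed settles on a compromise that is too shallow at Week 12, the visit of interest. The misfit goes into the Week 12 residual variance and so into the reported standard error. It also gives the check a different Baseline adjustment from the primary ANCOVA, whose slope is fitted to Week 12 alone.

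The companion question is what the page 1 skewness p-value is for. It comes from several correlated residuals per patient, but the test is built for independent observations, and the SAP does not say what follows from it.

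**Working it through.** The plan states no standard error, slope or residual count for this analysis, so there is no figure of its own to reproduce.

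**Inputs.** From the documents: 234 + 117 = 351 patients, 2:1; post-baseline visits at Weeks 2, 4, 8 and 12. Assumed: mean counts at those visits of 72, 58, 45 and 38% of Baseline on active and 85, 75, 66 and 62% on vehicle; an unstructured covariance; within-patient correlation 0.3–0.8.

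**1. Slope by visit.** If follow-up is a fraction f of Baseline, the slope of change on Baseline is −(1 − f). Pooled over arms at 2:1:
- Week 2: −(2 × 0.28 + 0.15)/3 = −0.24
- Week 4: −(2 × 0.42 + 0.25)/3 = −0.36
- Week 8: −(2 × 0.55 + 0.34)/3 = −0.48
- Week 12: −(2 × 0.62 + 0.38)/3 = −0.54

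The simple mean is −0.405. The generalized least-squares fit with one slope gave −0.35, which is 0.19 too shallow at Week 12.

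**2. Reported Week 12 standard error.** Simulated trials (234/117, Baseline 15–70, 400 per setting), common slope against visit-specific:
- 0.940 against 0.912: ratio 1.031
- 0.678 against 0.637: ratio 1.064
- 1.083 against 1.050: ratio 1.031

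A further simulation with 10% dropout gave 3–7%, with no meaningful shift in the estimate.

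**3. True precision.** In simulation the sampling SD fell only about 0.5–2%. The reason is that the assumed slopes also differ by arm (−0.62 active, −0.38 vehicle). With V the Baseline variance, the Baseline part of the true variance at a fitted slope β is V × [(−0.62 − β)²/234 + (−0.38 − β)²/117]:
- β = −0.35: 0.0729/234 + 0.0009/117 = 0.000319 V
- β = −0.54: 0.0064/234 + 0.0256/117 = 0.000246 V
- fall: 0.000073 V

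The reported variance pools residuals over arms and multiplies by 1/234 + 1/117 = 0.01282:
- β = −0.35: (2 × 0.0729 + 0.0009)/3 × 0.01282 = 0.000627 V
- β = −0.54: (2 × 0.0064 + 0.0256)/3 × 0.01282 = 0.000164 V
- fall: 0.000463 V

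The reported variance therefore falls about six times as much as the true one (0.000463/0.000073 = 6.3). If the common slope landed at the simple mean, −0.405, the true term would be 0.0462/234 + 0.0006/117 = 0.000203 V, already below 0.000246 V. The true gain is small and could be nil.

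**4. Skewness test.** Residuals: 351 × 4 = 1,404 with complete data at all four visits, or 351 × 3 = 1,053 with only the listed Weeks 2, 4 and 8. With exchangeable correlation ρ and four visits, the variance of sample skewness is inflated by about 1 + 3ρ³. At ρ = 0.6 this is 1 + 3 × 0.216 = 1.648. The 1% critical value of 2.576 then acts as 2.576/√1.648 = 2.01, a two-sided rate of about 4.5%. Simulation with symmetric residuals gave 2.4, 4.4, 6.4 and 9.0% at ρ = 0.5, 0.6, 0.7 and 0.8. Over ρ from 0.3 to 0.8 the range is about 1–9%. With three visits and ρ = 0.6 it gave 3.0%.

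**The case against.** **On the slope.** In a randomized comparison a common Baseline slope does not bias the treatment effect. The gain is a few percent of a standard error in a sensitivity analysis, under clearance percentages that are assumed, and section 10 shows that the sponsor had already revisited this model. All of that stands, and it limits the point to a small improvement. It does not justify the single slope, since the extra term costs nothing and brings the Baseline adjustment at Week 12 into line with the primary ANCOVA.

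**On the scale.** A reader might infer that page 1 uses its own skewness test to choose ranked or unranked, and so will often sit on a different scale from the primary analysis. The documents do not support this. No selection rule is written for the repeated-measures analysis. Both treatment p-values are printed there and in Table 14.2.1.2, so a same-scale comparison is always available.

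The word often would also need a residual skewness that the documents do not give. Suppose each analysis did choose by its own test at 0.01:
- With equal SDs and four visits, the two would disagree in 46–52% of trials at skewness 0.2 and 52–66% at 0.3, but in about 2% at 0.7 and none at 1.0.
- With the Phase 2 SDs (6.70 and 17.24) and the rough skewness implied by Phase 2 means and medians, the rate is 22–27%. Those skewness values are 3 × (15 − 14.1)/6.70 = 0.40 on active and 3 × (10 − 7.4)/17.24 = 0.45 on vehicle.

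**On page 2.** A reader might extend the correlation argument to the model-based imputation. It does not apply there, because those are single-visit ANCOVA residuals tested within each imputed dataset, as in the primary.

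**Conclusion.** The point holds as a minor one. With a single Baseline slope, the reported Week 12 standard error is about 3–7% larger than with visit-specific slopes. This rests on the assumed clearance and an unstructured covariance, and it shrinks if residual noise is large relative to the spread of Baseline counts. The gain in actual precision is about 0.5–2% in simulation, and possibly none. There is no bias.

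Separately, the page 1 skewness p-value is not at its nominal level (about 1–9% for a 1% test under the assumed correlations), and the SAP leaves open which printed treatment p-value is the sensitivity result. Neither matter touches the primary inference or the Type I error, and no result that a reader needs is missing from the table.

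**What to change.** Before unblinding:
- In SAP 8.7.2.1 and in footnotes a and c of Table 14.2.5.1 page 1, add the interaction of Baseline lesion count with visit.
- In the same places, state that this analysis is read on the scale selected for Table 14.2.1.2. Keep both treatment p-values printed, and remove the skewness column and footnote b from page 1. Leave page 2 as it is.
- While editing 8.7.2.1, reconcile the visit list with the use of all post-baseline visits and the Week 12 title.

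The cost is SAP wording and one model term: with four visits, four Baseline slopes instead of one, which is negligible with 351 patients. No new data are needed, and the primary analysis does not change.

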13. INDEX OF PLANNED FIGURES

Figure 14.2.3.1: Cumulative Distribution Function of Patient Assessment of Papulopustular Rosacea Signs and Symptoms (PAPSS) at Week 12 (Intent-to-Treat Population)	151
Figure 14.2.3.2: Cumulative Distribution Function of Patient Assessment of Papulopustular Rosacea Signs and Symptoms (PAPSS) at Week 12 (Per-Protocol Population)	156

[figure not shown]
Figure 14.2.3.1: Cumulative Distribution Function of Patient Assessment of Papulopustular Rosacea Signs and Symptoms (PAPSS) at Week 12
(Intent-to-Treat Population)
(Page 1 of 5)

Note: No imputation of missing values. Absolute Change calculated as Week 12 – Baseline. Negative values represent decrease from Baseline.

SOURCE: USERNAME\SPONSOR\PROJECT\JOBNAME (DATE,TIME)

Figure 14.2.3.1: Cumulative Distribution Function of Patient Assessment of Papulopustular Rosacea Signs and Symptoms (PAPSS) at Week 12
(Intent-to-Treat Population)
(Page 2 of 5)

Note: No imputation of missing values. Absolute Change calculated as Week 12 – Baseline. Negative values represent decrease from Baseline.

SOURCE: USERNAME\SPONSOR\PROJECT\JOBNAME (DATE,TIME)

[figure not shown]
Figure 14.2.3.1: Cumulative Distribution Function of Patient Assessment of Papulopustular Rosacea Signs and Symptoms (PAPSS) at Week 12
(Intent-to-Treat Population)
(Page 3 of 5)

Note: No imputation of missing values. Absolute Change calculated as Week 12 – Baseline. Negative values represent decrease from Baseline.

SOURCE: USERNAME\SPONSOR\PROJECT\JOBNAME (DATE,TIME)

[figure not shown]
Figure 14.2.3.1: Cumulative Distribution Function of Patient Assessment of Papulopustular Rosacea Signs and Symptoms (PAPSS) at Week 12
 (Intent-to-Treat Population)
 (Page 4 of 5)

Note: No imputation of missing values. Absolute Change calculated as Week 12 – Baseline. Negative values represent decrease from Baseline.

SOURCE: USERNAME\SPONSOR\PROJECT\JOBNAME (DATE,TIME)

Figure 14.2.3.1: Cumulative Distribution Function of Patient Assessment of Papulopustular Rosacea Signs and Symptoms (PAPSS) at Week 12
 (Intent-to-Treat Population)
 (Page 5 of 5)

Note: No imputation of missing values. Absolute Change calculated as Week 12 – Baseline. Negative values represent decrease from Baseline.

SOURCE: USERNAME\SPONSOR\PROJECT\JOBNAME (DATE,TIME)

Repeat Figure 14.2.3.1 for the following tables:

Figure 14.2.3.2: Cumulative Distribution Function of Patient Assessment of Papulopustular Rosacea Signs and Symptoms (PAPSS) at Week 12 (Per-Protocol Population)

xxxxxx	xxxx	xxxxxxxxxx	xxxxxxxxxxxxxxxxxxxx	xxxx	xxxxx xx xxxxx
xxxxxx	xxxx	xxxxxxxxxx	xxxxxxxxxxxxxxxxxxxx	xxxx	xxxxxxxx xxxxx
xxxxxx	xxxx	xxxxxxxxxx	xxxxxxxxxxxxxxxxxxxx	xxxx	xxxxx xx xxxxx
xxxxxx	xxxx	xxxxxxxxxx	xxxxxxxxxxxxxxxxxxxx	xxxx	xxxxxxxx xxxxx

SOURCE: USERNAME\SPONSOR\PROJECT\JOBNAME (DATE, TIME)

Listing sorted by Subject.

Listing 16.2.1.1: End of Study Information
 Treatment Arm
 (Page xx of yy)

Subject	Age/Sex	Eval	Date of First Application	Date of Last Application	Date of Study Completion/Discontinuation (Day) ¹	Did Subject Complete the Study	Primary Reason for Study Discontinuation	Continue to the Long Term Safety Study
xxxxxx	xxxx	xxxxxxxx	xxxxxxxxxx	xxxxxxxxxx	xxxxxxxxxxxxxxxx	xxx		xxx x xxx xxxxxx xxxx xxxxxxxx xxxxxxxxxxxx
xxxxxx	xxxx	xxxxxxxx	xxxxxxxxxx	xxxxxxxxxx	xxxxxxxxxxxxxxxx	xx	xxxxxxx xxxxx	xx x xxx xxxxxxxx xxxx xxx xxxxxxxx
xxxxxx	xxxx	xxxxxxxx	xxxxxxxxxx	xxxxxxxxxx	xxxxxxxxxxxxxxxx	xx	xxxx xx xxxxxxxxxxx xxxxxxxx xx xxxx xx xxxxxxxxxxxxxxx xxxxx xxxxxx xxxxx xxx xxxx	xx x xxx xxxxxxxx xxxx xxx xxxxxxxx

¹ Day is calculated as date - date of first application for dates prior to first application. Otherwise, day is calculated as date - date of first application + 1 for dates on or after first application.

SOURCE: USERNAME\SPONSOR\PROJECT\JOBNAME (DATE, TIME)

Listing sorted by Subject.

If Primary Reason for Study Discontinuation is Lost to Follow-Up, Protocol Violation, Withdrawal by Subject, or Other, the reason specification will be included following a colon (for example, WITHDRAWAL BY SUBJECT: xxxxx)

If subject will not continue to the LTS, the reason specification will be included in the final column following a colon.

Listing 16.2.2.1: Inclusion/Exclusion Criteria
 Treatment Group
 (Page xx of yy)

Subject	Age/Sex	Eval	Criterion Failed	Description
xxxxxx	xxxx	xxxxxxxxxx	xxxxxx	xxxxx xxx xx xxxxxxxx xxxx xxxxxxxxxxxxxxxxxxxxxxxx xxxxxxxx
xxxxxx	xxxx	xxxxxxxxxx	xxxxxx	xxxxx xxx xx xxxxxxxx xxxx xxxxxxxxxxxxxxxxxxxxxxxx xxxxxxxx
xxxxxx	xxxx	xxxxxxxxxx	xxxxxx	xxxxx xxx xx xxxxxxxx xxxx xxxxxxxxxxxxxxxxxxxxxxxx xxxxxxxx
			xxxxxx	xxxxx xxx xx xxxxxxxx xxxx xxxxxxxxxxxxxxxxxxxxxxxx xxxxxxxx
			xxxxxx	xxxxx xxx xx xxxxxxxx xxxx xxxxxxxxxxxxxxxxxxxxxxxx xxxxxxxx xxxxxxxxxxxxxxxxxxxx xxxxxxxxx x xxxxxxxxxxxxxxxxxxxx xxx

SOURCE: USERNAME\SPONSOR\PROJECT\JOBNAME (DATE, TIME)

Listing sorted by Subject and Criterion Failed.

Listing 16.2.2.2: Screen Failure
(Page xx of yy)

Subject	Age/Sex	Eval	Date of Screen Failure	Reason for Screen Failure
xxxxxx	xxxx	xxxxxxxxxx	xxxxxxxxxx	xxxxx xxx xx xxxxxxxx xxxx xxxxxxxxxxxxxxxxxxxxxxxx xxxxxxxx
xxxxxx	xxxx	xxxxxxxxxx	xxxxxxxxxx	xxxxx xxx xx xxxxxxxx xxxx xxxxxxxxxxxxxxxxxxxxxxxx xxxxxxxx
xxxxxx	xxxx	xxxxxxxxxx	xxxxxxxxxx	xxxxx xxx xx xxxxxxxx xxxx xxxxxxxxxxxxxxxxxxxxxxxx xxxxxxxx
			xxxxxxxxxx	xxxxx xxx xx xxxxxxxx xxxx xxxxxxxxxxxxxxxxxxxxxxxx xxxxxxxx
			xxxxxxxxxx	xxxxx xxx xx xxxxxxxx xxxx xxxxxxxxxxxxxxxxxxxxxxxx xxxxxxxx xxxxxxxxxxxxxxxxxxxx xxxxxxxx x xxxxxxxxxxxxxxxxxxxxxxx xxx

SOURCE: USERNAME\SPONSOR\PROJECT\JOBNAME (DATE, TIME)

Listing sorted by Subject.

Listing 16.2.2.3: Protocol Deviations
 Treatment Group
 (Page xx of yy)

Subject	Age/Sex	Eval	Deviation	Date (Day ¹)
xxxxxx	xxxx	xxxxxxxxxx	xxxxxx x xxxxxxxx xxx xx xxxxxx xxxxxx xxx xxx xx xxxxxxxxxxxxxx xxxxxx xxx xx xxxxxx xxxxxx xxx xxx xx xxxxxx x xxxxxxxx	xxxxxxxxxxxxxxxxxx xxxxxxxxxxxxxxxxxxx
xxxxxx	xxxx	xxxxxxxxxx	xxxxxx xxx xx xxxxxx xxxxxx xxx xxx xx	xxxxxxxxxxxxxxxxxx
xxxxxx	xxxx	xxxxxxxxxx	xxxxxx xxx xx xxxxxx xxxxxx xxx xxx xx	xxxxxxxxxxxxxxxxxx

¹ Day is calculated as date - Baseline date for dates prior to Baseline visit. Otherwise, day is calculated as date - Baseline date + 1 for dates on or after Baseline visit.

SOURCE: USERNAME\SPONSOR\PROJECT\JOBNAME (DATE, TIME)

Listing sorted by Subject and Date.

Listing 16.2.3: Analysis Populations
Treatment Group
(Page xx of yy)

Subject	Age/Sex	Population	Included	Reason(s)	Excluded	Exception(s)
xxxxxx	xxxx	Intent-to-Treat Safety Per-Protocol	xxx xxx xx		xxxxxxxxxxxx xxxxxxxx xxxxxxxx xxxxxxxxxxxx xxxxxxxx xxxxxxxx	
xxxxxx	xxxx	Intent-to-Treat Safety Per-Protocol	xxx xxx xxx		xxxxxxxxxxxx xxxxxxxx xxxxxxxx	xxxxxxxxxxxx xxxxxxxx xxxxxxxx
xxxxxx	xxxx	Intent-to-Treat Safety Per-Protocol	xxx xx xx		xxxxxxxxxxxx xxxxxxxx xxxxxxxx xxxxxxxxxxxx xxxxxxxx xxxxxxxx xxxxxxxxxxxx xxxxxxxx xxxxxxxx	

SOURCE: USERNAME\SPONSOR\PROJECT\JOBNAME (DATE, TIME)

Listing sorted by Subject and Population (as ordered above).

Listing 16.2.4.1: Subject Demographic Information
Treatment Arm
(Page xx of yy)

Subject	Eval	B: Date of Birth A: Age S: Sex	R: Race E: Ethnicity	C: Childbearing Potential M: Method of Birth Control	I: Informed Consent Date P: Photography Consent Signed
xxxxxx	xxxxxxxxxx	B: xxxx-xx-xx A: xx S: xxxxxx	R: xxxxxx xxxxxxxx xx xxxxx xxxxxxxx xxxxxxxxx xxxxxxxxxxxx E: xxx xxxxxxxx xx xxxxxx	C: xxx M: xxxxxxxxxxx xxxxxxxxxxx xxxxxxxxxxxxxxxx xxxxxxxxxxx xxxx x xxxxxxxxxxx xx xxxxxxxxx xxxxxxxxxxx xxxx xxxxxxx	I: xxxx-xx-xx P: xxx
xxxxxx	xxxxxxxxxx	B: xxxx-xx-xx A: xx S: xxx	R: xxxxx E: xxxxxxxx xx xxxxxx	C: xx M:	I: xxxx-xx-xx P: xx
xxxxxx	xxxxxxxxxx	B: xxxx-xx-xx A: xx S: xxxxxx	R: xxxxx E: xxxxxxxx xx xxxxxx	C: xxx M: xxxxxxxxxxx xxxxxxxxxxx	I: xxxx-xx-xx P: xx xxx x xxxxxxxxxxx xxxxx

SOURCE: USERNAME\SPONSOR\PROJECT\JOBNAME (DATE, TIME)

Listing sorted by Subject.

Listing 16.2.4.2.1: Unique Medical/Surgical History Coded to MedDRA System Organ Classes and Preferred Terms
(Page xx of yy)

MedDRA System Organ Class	MedDRA Preferred Term	Medical/Surgical History Verbatim Term
xxxx xxx xxxxxxxxxxx xxxxxx xxxxxxxxxxx	xxxxxxx	xxxxxx
	xxxx xxxxxxxxxxx xxxxxxxx	xxxx xxxxxxxxxxx xxxxxx
xxxxxxxxxxx xxx xxxxxxxxxxxxxx	xxxxxxxxxxxx	xxxxxxxxxxxx
	xxxxxxxxxxxxxxxx	xxxxxxxxxxxxxxxx x xxxx xxx xxx
		xxxxxxxxxxxxxxxx xx xxxxx xx xxxx xxxxx xxx

Note: System Organ Class and Preferred Term map to MedDRA (Version 21.0).

SOURCE: USERNAME\SPONSOR\PROJECT\JOBNAME (DATE, TIME)

Listing sorted by System Organ Class, Preferred Term, and Verbatim Term.

Listing 16.2.4.2.2: Medical/Surgical History
Treatment Arm
(Page xx of yy)

Subject	Age/Sex	Eval	Medical/Surgical History Verbatim Term	S: MedDRA System Organ Class P: MedDRA Preferred Term	S: Onset Date E: End Date
xxxxxx	xxxx	xxxxxxxx	xxxxxx	S: xxxx xxx xxxxxxxxxxxxxx xxxxxx xxxxxxxxxxx P: xxxxxxxx	S: xxxx E:
			xxxxxxxx xx xxxxxxxxxxxxxx xxxxxxxxxxx	S: xxxxxx xxxxxx xxxxxxxxxxx P: xxxxxxxx xxxxxx xxxxxxxx	S: xxxx E: xxxxxxxx
xxxxxx	xxxx	xxxxxxxx	xxxxxx	S: xxxx xxx xxxxxxxxxxxxxx xxxxxx xxxxxxxxxxx P: xxxxxxxx	S: xxxx E:
xxxxxx	xxxx	xxxxxxxx	xxxxxx	S: xxxx xxx xxxxxxxxxxxxxx xxxxxx xxxxxxxxxxx P: xxxxxxxx	S: xxxx E:
xxxxxx	xxxx	xxxxxxxx	xxxxxx	S: xxxx xxx xxxxxxxxxxxxxx xxxxxx xxxxxxxxxxx P: xxxxxxxx	S: xxxx E:
			xxxxxxxxxxxxxxxxxxxx	S: xxxxxx xxxxxx xxx P: xxxx xxxxxxxxxxxxxx	S: xxxxxxxxxxx E: xxxxxxxx

Note: System Organ Class and Preferred Term map to MedDRA (Version 21.0).

SOURCE: USERNAME\SPONSOR\PROJECT\JOBNAME (DATE, TIME)

Listing sorted by Subject, Rosacea Diagnosis (all Rosacea MH will appear first), Onset Date, End Date, Verbatim Term

Listing 16.2.4.3.1: Unique Medication Names Coded to WHO Drug Global Dictionary ATC Level 2 Terms and Preferred Names
(Page xx of yy)

WHO ATC Level 2 Term	WHO Preferred Name	Medication Verbatim Term	I: Indication T: Route
xxxxxxxxxxxxxxxx	xxxxxxxxxxxxxxxx	xxxxxxx	I: xxxxxxxxxxx R: xxxxxxxxxxx
		xxxxxxx	I: xxxxxxxxxxx R: xxxxxxxxxxx
xxxxxxxxxxxxxxxx	xxxxxxxxxxxxxxxx	xxxxxxx	I: xxxxxxxxxxx R: xxxxxxxxxxx
		xxxxxxx	I: xxxxxxxxxxx R: xxxxxxxxxxx

Note: ATC Level 2 Term and Preferred Name map to WHO Drug Global Dictionary, Format B3, Version March 1, 2018.

SOURCE: USERNAME\SPONSOR\PROJECT\JOBNAME (DATE, TIME)

Listing sorted by ATC Level 2 Term, Preferred Name, Medication Verbatim Term, Indication, and Route.

Listing 16.2.4.3.2: Prior and Concomitant Medications
Treatment Arm
(Page xx of yy)

S: Subject	A: ATC Level 2 Term	S: Start Date (Day) ¹	I: Indication	F: Frequency
A: Age/Sex	P: Preferred Name	E: End Date (Day) ¹	D: Dose	T: Route
E: Eval	M: Medication Name	P: Prior/Concomitant	U: Units	

S: xxxxxx	A: xxxxxxxxxxx xxx xxxxxxxxxxx	S: xxxxxxxxxxxxxxxxxxx	I: xxxxxxx	F: xx
A: xxxx	P: xxxxxxxxxxx xxxxxxx xxxxxxxxxxxxxx xxx xxxxxxx xxx	E: xxxxxxxxxxxxxxxxxxx	D: xx	T: xxxxxxxxxxxxxxxxxxx
E: xxxxxxxxxxx	M: xxxxxx xxxxx xxxxxxxxxxx	P: xxxxxxxxxxxxxxxxxxxxxx	U: xxxxxxxxxxx	
	A: xxxxxxxx xx xxxxxxxx	S: xxxxxxxxxxxxxxxxxxx	I: xxxxxxx	F: xx
	P: xxxxxxxxxxx xxxxxxx xxx	E: xxxxxxxxxxxxxxxxxxx	D: xx	T: xxxxxx
	M: xxxxxx xxxxxxxxxxx	P: xxxxxx	U: xxxxxxxx	
S: xxxxxx	A: xxxxxxxxxxx xxx xxxxxxxxxxx	S: xxxxxxxxxxxxxxxxxxx	I: xxxxxxx	F: xx
A: xxxx	P: xxxxxxxxxxx xxxxxxx xxxxxxxxxxxxxx xxx xxxxxxx xxx	E: xxxxxxxxxxxxxxxxxxx	D: xx	T: xxxxxxxxxxxxxxxxxxx
E: xxxxxxxxxxx	M: xxxxxx xxxxx xxxxxxxxxxx	P: xxxxxxxxxxxxxxxxxxxxxx	U: xxxxxxxxxxx	
	A: xxxxxxxx xx xxxxxxxx	S: xxxxxxxxxxxxxxxxxxx	I: xxxxxxx	F: xx
	P: xxxxxxxxxxx xxxxxxx xxx	E: xxxxxxxxxxxxxxxxxxx	D: xx	T: xxxxxx
	M: xxxxxx xxxxxxxxxxx	P: xxxxxx	U: xxxxxxxx	

¹ Day is calculated as date - date of first application for dates prior to first application. Otherwise, day is calculated as date - date of first application + 1 for dates on or after first application.

Note: ATC Level 2 Term and Preferred Name map to WHO Drug Global Dictionary, Format B3, Version March 1, 2018.

SOURCE: USERNAME\SPONSOR\PROJECT\JOBNAME (DATE, TIME)

Listing sorted by Subject, Start Date, End Date, Medication Name, Indication, Route, Frequency. If the Route is Topical, then the area treated is presented within parenthesis (T: Topical (specify area)).

Listing 16.2.4.4.1: Unique Procedure/Therapy Names Coded to MedDRA System Organ Classes and Preferred Terms
(Page xx of yy)

MedDRA System Organ Class	MedDRA Preferred Term	Procedure/Therapy Verbatim Term	Indication
xxxxxxxxxxxxxxxx	xxxxxxxxxxxxxxxx	xxxxxxxx xx xxxxx	xxxxxxxxxxxx
		xxxxxxxxxx	xxxxx xx xxxxx
xxxxxxxxxxxxxxxx	xxxxxxxxxxxxxxxx	xxxxxxxxxx	xxxxxxxxxx
		xxxxxxxxxx	xxxxxxxxxxxx
xxxxx xxx xx xxxxxxx	xxxxxxx xxxxxxx xxxxx	xxxxxxxxxx xxxxxxx	xxxxxxxxxx xxxxxxxxx xx xx xxxxx

Note: System Organ Class and Preferred Term map to MedDRA (Version 21.0).

SOURCE: USERNAME\SPONSOR\PROJECT\JOBNAME (DATE, TIME)

Listing sorted by System Organ Class, Preferred Term, Verbatim Term, and Indication.

Listing 16.2.4.4.2: Prior and Concomitant Procedures/Therapies
Treatment Arm
(Page xx of yy)

Subject	Age/Sex	Eval	S: MedDRA System Organ Class P: MedDRA Preferred Term M: Procedure/Therapy Name	S: Start Date (Day) ¹ E: End Date (Day) ¹ P: Prior/Concomitant	I: Indication A: Anatomical Area Treated
xxxxxx	xxxx	xxxxxxxx	S: xxxxxxxx xxx xxxxxxxx xxxxxxxx P: xxxxxxxxxxxx xxxxxxxxxxxx xxxxxxxx M: xxxxxxxx xxxxxx xxxxxxxx xxxxxxxx	S: xxxxxxxxxxxxxxxxxxxxxxxx E: xxxxxxxxxxxxxxxxxxxxxxxx P: xxxxxxxxxxxxxxxxxxxxxxxx	I: xxxxxx xxxxxxxx A:
xxxxxx	xxxx	xxxxxxxx	S: xxxxxxxx xxx xxxxxxxx xxxxxxxx P: xxxxxxxxxxxx xxxxxxxxxxxx xxxxxxxx M: xxxxxxxx xxxxxx xxxxxxxx xxxxxxxx	S: xxxxxxxxxxxxxxxxxxxxxxxx E: xxxxxxxxxxxxxxxxxxxxxxxx P: xxxxxxxxxxxxxxxxxxxxxxxx	I: xxxxxx xxxxxxxx A:
xxxxxx	xxxx	xxxxxxxx	S: xxxxxxxx xxx xxxxxxxx xxxxxxxx P: xxxxxxxxxxxx xxxxxxxxxxxx xxxxxxxx M: xxxxxxxx xxxxxx xxxxxxxx xxxxxxxx	S: xxxxxxxxxxxxxxxxxxxxxxxx E: xxxxxxxxxxxxxxxxxxxxxxxx P: xxxxxxxxxxxxxxxxxxxxxxxx	I: xxxxxx xxxxxxxx A:
			S: xxxxxxxx xxxxxxxx xxxxx P: xxx xxxxxxxxxxxx xxxxxxxx M: xxxxxxxx xxxxxxxx	S: xxxxxxxxxxxxxxxxxxxxxxxx E: xxxxxxxxxxxxxxxxxxxxxxxx P: xxxxxxxxxxxxxxxxxxxxxxxx	I: xxxxxxxxxxxx xxxxxx xx xx A: xxxxxxxxxxxx
			S: xxxxxxxx xxxxxxxx xxxxx P: xxx xxxxxxxxxxxx xxxxxxxx M: xxxxxxxx xxxxxxxx	S: xxxxxxxxxxxxxxxxxxxxxxxx E: xxxxxxxxxxxxxxxxxxxxxxxx P: xxxxxxxxxxxxxxxxxxxxxxxx	I: xxxxxxxxxxxx xxxxxx xx xx A: xxxxxxxxxxxx

¹ Day is calculated as date - date of first application for dates prior to first application. Otherwise, day is calculated as date - date of first application + 1 for dates on or after first application.

Note: System Organ Class and Preferred Term map to MedDRA (Version 21.0).

SOURCE: USERNAME\SPONSOR\PROJECT\JOBNAME (DATE, TIME)

Listing sorted by Subject, Start Date, End Date, Procedure/Therapy Name, and Indication.

Listing 16.2.5.1: Study Visit Compliance
Treatment Arm
(Page xx of yy)

Subject	Age/Sex	Eval	Visit	Visit Date	Study Day ¹	Within Visit Window ²	Reason Screening And Baseline Occurred on Different Days	Reason for Unscheduled Visit
xxxxxx	xxxx	xxxxxxxx	xxxxxxxx	xxxxxxxx	xx	xxx		
			xxxxxxxx	xxxxxxxx	xx	xxx	xxxxxxxx xxx xx	
			xxxx x	xxxxxxxx	xx	xxx	xxxxxxxx	
			xxxx x	xxxxxxxx	xx	xxx		
			xxxx x	xxxxxxxx	xx	xxx		
			xxxx xxxxx	xxxxxxxx	xx	xxx		
xxxxxx	xxxx	xxxxxxxx	xxxxxxxx	xxxxxxxx	xx	xxx		
			xxxxxxxx	xxxxxxxx	xx	xxx		
			xxxx x	xxxxxxxx	xx	xxx		
			xxxx x	xxxxxxxx	xx	xxx		
			xxxxxxxxxxxx xxxxx xxx	xxxxxxxx	xx	xxx		xxxxxxxxxxxx
			xxxx x	xxxxxxxx	xx	xxx		
			xxxx xxxxx	xxxxxxxx	xx	xxx		
xxxxxx	xxxx	xxxxxxxx	xxxxxxxx	xxxxxxxx	xx	xxx		
			xxxxxxxx	xxxxxxxx	xx	xxx		
			xxxx x	xxx xxx	xx	xxx		xxx xxx
			xxxx x	xxx xxx	xx	xxx		xxx xxx
			xxxx x	xxxxxxxx	xx	xxx		
			xxxx xxxxx	xxxxxxxx	xx	xxx		

¹ Day is calculated as date - Baseline date for dates prior to Baseline visit. Otherwise, day is calculated as date - Baseline date + 1 for dates on or after Baseline visit.

² Determined by protocol-specified visit window for scheduled visits after Baseline.

SOURCE: USERNAME\SPONSOR\PROJECT\JOBNAME (DATE, TIME)

Listing sorted by Subject and Visit Number.

Listing 16.2.5.2: Subject Dosing Compliance
Treatment Arm
(Page xx of yy)

Subject	Age/Sex	Eval	Date of First Application	Date of Last Application	Number of Days of Exposure	Calculated ¹ Number of Applications	Amount of Study Drug Used (g)	Maximum Number of Consecutive Missed Applications	Percent Compliant	Compliant ²
xxxxxx	xxxx	xxxxxxxx	xxxxxxxxxx	xxxxxxxxxx	xx	xx	xxxx	xx	xxxxx	xxx
xxxxxx	xxxx	xxxxxxxx	xxxxxxxxxx	xxxxxxxxxx	xx	xx	xxxx	xx	xxxxx	xxx
xxxxxx	xxxx	xxxxxxxx	xxxxxxxxxx	xxxxxxxxxx	xx	xx	xxxx	xx	xxxxx	xxx
xxxxxx	xxxx	xxxxxxxx	xxxxxxxxxx	xxxxxxxxxx	xx	xx	xxxx	xx	xxxxx	xxx
xxxxxx	xxxx	xxxxxxxx	xxxxxxxxxx	xxxxxxxxxx	xx	xx	xxxx	xx	xxxxx	xxx

¹ The total number of applications was calculated using the date of first application, date of last application, and number of applied applications at a deviation.

² A subject was considered compliant with the dosing regimen if the subject did not miss more than 5 consecutive days applying and applied 80-120% of expected applications based on the length of their participation in the study.

SOURCE: USERNAME\SPONSOR\PROJECT\JOBNAME (DATE, TIME)

Listing sorted by Subject.

Listing 16.2.5.3: Subject Dosing Deviations
Treatment Arm
(Page xx of yy)

Subject	Age/Sex	Eval	Date of Dosing Deviation (Day) ¹	Number of Applications Applied
xxxxxx	xxxx	xxxxxxx	xxxxxxxxxxxxx xxxxxxxxxxxxx	x x
xxxxxx	xxxx	xxxxxxx	xxxxxxxxxxxxx	x
xxxxxx	xxxx	xxxxxxx	xxxxxxxxxxxxx xxxxxxxxxxxxx xxxxxxxxxxxxx xxxxxxxxxxxxx xxxxxxxxxxxxx xxxxxxxxxxxxx xxxxxxxxxxxxx	x x x x x x x
xxxxxx	xxxx	xxxxxxx	xxxxxxxxxxxxx xxxxxxxxxxxxx	x x
xxxxxx	xxxx	xxxxxxx	xxxxxxxxxxxxx	x

¹ Day is calculated as date - date of first application for dates prior to first application. Otherwise, day is calculated as date - date of first application + 1 for dates on or after first application.

SOURCE: USERNAME\SPONSOR\PROJECT\JOBNAME (DATE, TIME)

Listing sorted by Subject and Date of Dosing Deviation.

Listing 16.2.5.4: Study Medication Accountability Log
 Treatment Arm
 (Page xx of yy)

Subject	Age/Sex	Eval	Kit Number	Kit Contents	Pump Identifier	Dispensing		Return		Amount Used (g)
						Date	Weight (g)	Date	Weight (g)	
xxxxxx	xxxx	xxxxxxxx	xxxx	xxxx	x	xxxxxxxxxx	xxxx	xxxxxxxxxx	xxxx	xxxx
				xxxx	x	xxxxxxxxxx	xxxx	xxxxxxxxxx	xxxx	xxxx
				xxxx	x	xxxxxxxxxx	xxxx	xxxxxxxxxx	xxxx	xxxx
				xxxx	x	xxxxxxxxxx	xxxx	xxxxxxxxxx	xxxx	xxxx
xxxxxx	xxxx	xxxxxxxx	xxxx	xxxx	x	xxxxxxxxxx	xxxx	xxxxxxxxxx	xxxx	xxxx
				xxxx	x	xxxx xxxx		xxxx xxxx		
				xxxx	x	xxxxxxxxxx	xxxx	xxxxxxxxxx	xxxx	xxxx
				xxxx	x	xxxxxxxxxx	xxxx	xxxxxxxxxx	xxxx	xxxx
xxxxxx	xxxx	xxxxxxxx	xxxx	xxxx	x	xxxxxxxxxx	xxxx	xxxxxxxxxx	xxxx	xxxx
				xxxx	x	xxxxxxxxxx	xxxx	xxxxxxxxxx	xxxx	xxxx
				xxxx	x	xxxxxxxxxx	xxxx	xxxxxxxxxx	xxx xxxx	xxxx
				xxxx	x	xxxxxxxxxx	xxxx	xxxxxxxxxx	xxxx	xxxx

SOURCE: USERNAME\SPONSOR\PROJECT\JOBNAME (DATE, TIME)

Note to programmers: Kit Contents is the treatment the kit contained.

Listing 16.2.5.5: Photography
 Treatment Arm
 (Page xx of yy)

Subject	Age/Sex	Eval	Visit	Were Photographs Taken	Date Taken
xxxxxx	xxxx	xxxxxxxx	xxxxxxxx	xxx	xxxxxxxxxx
			xxxx x	xxx	xxxxxxxxxx
			xxxx x	xx	
			xxxx x	xxx	xxxxxxxxxx
			xxxx xxxxx	xxx	xxxxxxxxxx
xxxxxx	xxxx	xxxxxxxx	xxxxxxxx	xxx	xxxxxxxxxx
			xxxx x	xxx	xxxxxxxxxx
			xxxx x	xxx	xxxxxxxxxx
			xxxx x	xxx	xxxxxxxxxx
			xxxxxxxxxxxx xxxxx xxx	xxx	xxxxxxxxxx
			xxxx xxxxx	xx	
xxxxxx	xxxx	xxxxxxxx	xxxxxxxx	xxx	xxxxxxxxxx
			xxxx x	xxx	xxxxxxxxxx
			xxxx x	xxx	xxxxxxxxxx
			xxxx x	xxx	xxxxxxxxxx
			xxxx xxxxx	xxx	xxxxxxxxxx

SOURCE: USERNAME\SPONSOR\PROJECT\JOBNAME (DATE, TIME)

Listing sorted by Subject and Visit Number

Listing 16.2.6.1: Investigator Global Assessment
 Treatment Arm
 (Page xx of yy)

Subject	Age/Sex	Eval	Visit	Date of Assessment	Evaluator Initials	Result
xxxxxx	xxxx	xxxxxxxx	xxxxxxxx xxxx x xxxx x xxxx x xxxx xxxxx	xxxxxxxx xxxxxxxx xxxxxxxx xxxxxxxx xxxxxxxx	xxx xxx xxx xxx xxx	xxxxxxxx xxxxxxxx xxxxxxxx xxxxxxxx xxxxxxxx
xxxxxx	xxxx	xxxxxxxx	xxxxxxxx xxxx x xxxx x xxxx x xxxx xxxxx	xxxxxxxx xxxxxxxx xxxxxxxx xxxxxxxx xxxxxxxx	xxx xxx xxx xxx xxx	xxxxxxxx xxxxxxxx xxxxxxxx xxxxxxxx xxxxxxxx
xxxxxx	xxxx	xxxxxxxx	xxxxxxxx xxxx x xxxx x xxxx x xxxx xxxxx	xxxxxxxx xxxxxxxx xxxxxxxx xxxxxxxx xxxxxxxx	xxx xxx xxx xxx xxx	xxxxxxxx xxxxxxxx xxxxxxxx xxxxxxxx xxxxxxxx

SOURCE: USERNAME\SPONSOR\PROJECT\JOBNAME (DATE, TIME)

Listing sorted by Subject and Visit Number

Listing 16.2.6.2: Inflammatory Lesion Counts
 Treatment Arm
 (Page xx of yy)

Subject	Age/Sex	Eval	Visit	Date of Assessment	Evaluator Initials	Papules	Pustules	Total Inflammatory Lesion Count	Nodules/Cysts
xxxxxx	xxxx	xxxxxxxx	xxxxxxxx	xxxxxxxx	xxx	xx	xx	xx	x
			xxxx x	xxxxxxxx	xxx	xx	xx	xx	x
			xxxx x	xxxxxxxx	xxx	xx	xx	xx	x
			xxxx x	xxxxxxxx	xxx	xx	xx	xx	x
			xxxx xxxxx	xxxxxxxx	xxx	xx	xx	xx	x
xxxxxx	xxxx	xxxxxxxx	xxxxxxxx	xxxxxxxx	xxx	xx	xx	xx	x
			xxxx x	xxxxxxxx	xxx	xx	xx	xx	x
			xxxx x	xxxxxxxx	xxx	xx	xx	xx	x
			xxxx x	xxxxxxxx	xxx	xx	xx	xx	x
			xxxx xxxxx	xxxxxxxx	xxx	xx	xx	xx	x
xxxxxx	xxxx	xxxxxxxx	xxxxxxxx	xxxxxxxx	xxx	xx	xx	xx	x
			xxxx x	xxxxxxxx	xxx	xx	xx	xx	x
			xxxx x	xxxxxxxx	xxx	xx	xx	xx	x
			xxxx x	xxxxxxxx	xxx	xx	xx	xx	x
			xxxx xxxxx	xxxxxxxx	xxx	xx	xx	xx	x
xxxxxx	xxxx	xxxxxxxx	xxxxxxxx	xxxxxxxx	xxx	xx	xx	xx	x
			xxxx x	xxxxxxxx	xxx	xx	xx	xx	x
			xxxx x	xxxxxxxx	xxx	xx	xx	xx	x
			xxxx x	xxxxxxxx	xxx	xx	xx	xx	x
			xxxx xxxxx	xxxxxxxx	xxx	xx	xx	xx	x

SOURCE: USERNAME\SPONSOR\PROJECT\JOBNAME (DATE, TIME)

Listing sorted by Subject and Visit Number

Listing 16.2.6.3.1: RosaQoL Descriptions
(Page xx of yy)

Number	RosaQoL Question
1	I worry that my rosacea may be serious
2	My rosacea burns or stings
3	I worry about getting scars from my rosacea
4	I worry that my rosacea may get worse
5	I worry about side effects from rosacea medications
6	My rosacea is irritated
7	I am embarrassed by my rosacea
8	I am frustrated by my rosacea
9	My rosacea makes my skin sensitive
10	I am annoyed by my rosacea
11	I am bothered by the appearance of my skin (redness, blotchiness)
12	My rosacea makes me feel self-conscious
13	I try to cover up my rosacea (with make-up)
14	I am bothered by persistence/reoccurrence of my rosacea
15	I avoid certain foods or drinks because of my rosacea
16	My skin feels bumpy (uneven, not smooth, irregular)

